**Table 3. Estimated Probability of TIE when  $\beta=1$**

Dose ( $d$ ) ( $\mu\text{g/kg}$ )	Estimated TIE Rate	Adjusted Dose ( $x$ )
1	2.5%	-1.83
2	3.3%	-1.69
3	4.5%	-1.53
4	6%	-1.38
5*	8%	-1.22
6	10.5%	-1.07
8	13.5%	-0.93
10	17.5%	-0.78
12	22%	-0.63
15	27%	-0.50
19	32.5%	-0.37
24	38%	-0.24
30	43%	-0.14
37	49%	-0.02
47	55%	0.10

\* starting dose

*Like all Bayesian methods, the adopted mCRM design may be sensitive to prior information placed on the model parameter  $\beta$  at the beginning of the trial. However, as the trial progresses and the TIE data accumulates, it eventually overrules the prior information and later becomes less important.*

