## 1. VERSION HISTORY

The first version of the Statistical Analysis Plan (SAP) for study B2341002 was based on the protocol amendment 1 dated 28 June 2016. This SAP amendment reflects changes made to the protocol to ensure that the analyses described are consistent with those described in the study protocol amendment 2 dated 17 January 2017.

Pfizer made the decision to terminate the study early after 21 subjects were enrolled in the study in October 2017. Changes in the analyses plan reflect this early study termination.

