## 2.2. Study Design

*This is a Phase 1b, multi-center, open-label study to determine the maximum tolerated dose (MTD) and assess the safety and tolerability, and PD of PF-05230907 administered once as an IV bolus in subjects with ICH. A modified continual reassessment method (mCRM) design based on the endpoints of treatment emergent thromboembolic and/or ischemic events (TIEs) will be adopted. The mCRM design utilizes Bayesian methodology to continuously learn the dose-toxicity relationship, which is characterized by a parametric model. The starting dose will be 5 µg/kg based on the highest dose safely administered in the first in human (FIH) clinical study (B2341001). As safeguards for subject safety, dose escalation will be conducted in a limited number of subjects per cohort (N=3). Sequential dosing criteria will be assessed for each cohort, dosing will be paused following completion of each cohort, internal safety monitoring and external Data Monitoring Committee (eDMC) review of the safety data will be conducted. The total length of time planned for study participation is approximately 3 months; 6.0 hours for screening, a single dose administration with a 4 day minimum hospital confinement period and follow-up visits through Day 91.*

The determination of MTD using mCRM dose-toxicity modeling will be based on TIEs which occur through 7 days post-dose (Day 8). *A target 15% TIE rate at the MTD will be employed for the MTD determination. The range of doses that may be explored will be from a grid of doses ranging from 1 µg/kg to 47 µg/kg. Subjects will be enrolled in cohorts of 3, starting with an initial dose of 5 µg/kg for the first cohort. If the modeled rate of TIEs at the 5 µg/kg starting dose exceeds the pre-specified target toxicity rate of 15% for the MTD, lower doses may be explored. Starting with the second cohort, subjects will be assigned to a dose in the pre-defined dose grid that is closest to, but not exceeding, the currently predicted MTD based on a parametric dose-toxicity model that the mCRM utilizes to learn about the overall dose-TIE relationship subject to additional dose escalation constraints and clinical oversight. The dose-toxicity model is updated based on the frequency of TIEs in each completed cohort. Under the adopted mCRM design, the dose level for each subsequent cohort can be escalated, deescalated, or restudied but always aiming towards the MTD target based on the frequency of TIEs.*

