#### 5.2.4. Stopping Rule

The dose-toxicity model is updated based on the frequency of TIEs in each completed cohort. This process is continued until at least one of the following stopping rules is met:

1. Maximum sample size of 51 subjects has been reached.
2. MTD has been identified with sufficient accuracy, ie, 12 subjects have been accumulated on a dose that is currently estimated to be the MTD by the fitted dose-toxicity curve.
3. All doses appear to be overly toxic and the MTD cannot be determined in the current trial setting (stop for futility).

If the stopping rule 1 is met but the stopping rule 2 is not met, not enough subjects have been studied to yield a model-based estimated MTD. If the stopping rule 2 is met, then the MTD will be identified as the current model-based estimated MTD. The earliest time point at which the trial could be stopped early and declare an MTD is after 20 subjects have been

treated and 12 at the MTD dose. For stopping rule 3, the futility stop can be made at any time.

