#### 5.2.5. Simulation for mCRM Design

*Extensive simulations were performed to compare the operating characteristics of various competing mCRM designs in order to fine-tune mCRM performance and choose the 'best' mCRM design. Below is a brief description of the simulation setup and key findings. All the simulations were performed in ADE (v3.0.2.1).*

*Different combinations of cohort sizes (2 or 3), maximum dose escalation allowed between cohorts (1, 2 or 3 doses), stopping rules (maximum number of 6, 9, 12, 15, 18 and 24 subjects on MTD), mCRM dose-toxicity model (power or hyperbolic-tangent), and starting dose (5 µg/kg or 8 µg/kg) were examined. Competing designs were evaluated under 6 different plausible scenarios of dose-TIE curves varying in steepness, location of the true MTD and overall toxicity level in the range of the dosing grid.*

*For each of the above competing designs, the operating characteristics were compared by scenario to evaluate the trade-off between precision of MTD estimation and study efficiency. The final chosen design is a mCRM design with cohort size of 3, a starting dose of 5 µg/kg, and the stopping rule with maximum 12 subjects on MTD using the hyperbolic-tangent dose-toxicity working model. Based on simulations, this design provides, on average, a more accurate estimate of MTD and comparable or less proportion of subjects receiving doses higher than the MTD than the conventional 3+3 design, with an acceptable increase in the average sample size. Details of the simulations were documented in a simulation report for this study.*

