### 6.1. Primary Endpoints

#### 6.1.1. Treatment emergent TIEs through Day 8

The primary analyses will be based on the TIE-evaluable set. Treatment emergent TIEs will be listed and summarized overall and by dose group. The summary Tables include:

- Treatment emergent TIEs (all causalities) by system organ class and preferred term
- Treatment emergent TIEs (treatment related) by system organ class and preferred term
- Incidence and severity of treatment emergent TIEs (all causalities, treatment related)

As discussed in Section 5.2, the TIE data from the current cohort (and previous cohort[s]) will be utilized for the mCRM dose-toxicity modeling along with clinical and eDMC oversight to determine the MTD. The following Figures will be generated:

- Vertical bar chart of the number of treatment emergent TIEs by dose group used in the mCRM dose-toxicity modeling
- Estimated Dose-TIE toxicity response curve with 95% confidence interval around the fitted curve, superimposed on the number of subjects allocated to each dose group in a vertical bar chart format, and the observed proportion of treatment emergent TIE at each dose level
- Allocation of subjects at each dose and corresponding TIE toxicity response (red dot denotes treatment emergent TIE) showing how dose-escalation scheme progresses over time via the order of study enrollment and observed number of treatment emergent TIEs

For the interim analysis of the treatment emergent TIEs, refer to Section 7 for details.

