#### **6.1.1.1. Sensitivity/Robustness Analyses**

One primary objective of this study is to determine the MTD of the study drug. The mCRM dose-toxicity modeling is based on an “intent-to-treat” approach that the subject’s assigned dose group is used in the modeling, estimation of MTD, and dose-recommendation for the next cohort based on available data during the safety review period after each respective cohort completes dosing. Sensitivity analysis will be conducted to assess the robustness of the MTD determination based on weight-based dosing. A confidence interval around the MTD may be calculated where appropriate. The relationship of the actual dose administered in  $\mu\text{g}$  with treatment emergent TIE occurrence will also be evaluated.

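### The SAP plans no refit under a second prior, although at 21 subjects the prior can still move the fitted dose and the limit beta ≤ 3 can set one end of the reported interval

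*SAP*

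**What the plan says.** SAP 5.2.2 gives one prior, Unif[0,3] on beta, together with the Table 3 rates at beta = 1. It concedes possible sensitivity to that prior and relies on accumulating data: "as the trial progresses and the TIE data accumulates, it eventually overrules the prior information and later becomes less important". SAP 2.2 says "The range of doses that may be explored will be from a grid of doses" running from 1 to 47 µg/kg.

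SAP 1 records the decision to "terminate the study early after 21 subjects were enrolled in the study in October 2017". The maximum in SAP 2.2.1 is 51. SAP 6.1.1 still plans an "Estimated Dose-TIE toxicity response curve with 95% confidence interval around the fitted curve", and SAP 6.1.1.1 adds: "A confidence interval around the MTD may be calculated where appropriate".

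The sensitivity analyses concern dose and evaluability:

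- SAP 6.1.1.1: "Sensitivity analysis will be conducted to assess the robustness of the MTD determination based on weight-based dosing"
- SAP 6.5.3: the actual dose administered.
- SAP 4.2.1: replacement subjects.

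None refits the model under another prior. The simulation factors named in SAP 5.2.5 are "Different combinations of cohort sizes (2 or 3), maximum dose escalation allowed between cohorts (1, 2 or 3 doses), stopping rules", working model and starting dose. The prior is not on that list. SAP 5.2.5 calls itself a brief description, and the simulation report is not among the documents.

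SAP 5.2.4 limits what can be claimed. If the maximum sample size is reached without 12 subjects on the estimated dose, "not enough subjects have been studied to yield a model-based estimated MTD".

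**The concern.** The SAP's answer to prior sensitivity is that data will wash the prior out. The trial ended at fewer than half of its maximum subjects, so that answer needs checking at the size actually reached. The amendment that followed termination dropped several analyses because of the small sample, but it kept the fitted dose-TIE curve and its interval, the model output most exposed to the prior.

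There is also a structural limit. A uniform prior that stops at 3 gives no weight to any larger beta, so no amount of data can move the fit beyond it. If few TIEs occur, one end of a reported 95% interval may simply be this boundary while looking like information from the subjects.

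**Working it through.** **Inputs.** From the documents: the Table 3 rates p, the prior Unif[0,3], the 15% target, the posterior-mean plug-in and the rule taking the highest grid dose below the estimate (SAP 5.2.3), cohorts of 3, start at 5 µg/kg, at most two increments above the highest dose studied, and 21 subjects = 7 cohorts. Assumed: the true curves, the alternative priors, no sponsor or eDMC override, and the 95% interval taken as posterior quantiles of beta passed through the curve (the SAP does not define it).

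**Reproducing the plan's figures.** With beta = 1, x = atanh(2p − 1). For p = 2.5%, 8% and 55% this gives −1.83, −1.22 and 0.10, and all 15 values in Table 3 match. Also 51/3 = 17 cohorts.

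**The model.** Because (1 + tanh x)/2 = p, the fitted rate at a dose is p^beta. The fitted dose is the highest grid dose with p < 0.15^(1/posterior mean of beta).

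**The ceiling.** With beta ≤ 3, the lowest possible fitted rates are:

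- 30 µg/kg: 0.43³ = 8.0%
- 47 µg/kg: 0.55³ = 16.6%, above the 15% target.

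A fitted MTD of 47 µg/kg needs beta > ln 0.15/ln 0.55 = 3.17, so the top grid dose can never be the fitted MTD.

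**Enumeration at 21 subjects.** Every seven-cohort path under Unif[0,3] was followed exactly and its final data refitted. Paths in which all doses appear too toxic were excluded (3.0, 0.2, 0.0 and 0.0% of trials). True rates are Table 3 raised to the power beta.

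| Share of trials | beta 1 | 1.5 | 2 | 2.5 |
|---|---|---|---|---|
| Dose changes, gamma (mean 1.5, variance 0.75) | 26% | 41% | 45% | 48% |
| Dose changes, exponential mean 1 | 60% | 58% | 45% | 41% |
| Dose changes, Unif[0,5] | 6% | 33% | 66% | 86% |
| Two or more steps, exponential or Unif[0,5] | 0.3% | 5% | 21% | 43% |
| Upper 95% limit of beta above 2.9 under Unif[0,3] | 3% | 28% | 64% | 86% |

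The gamma prior is matched to Unif[0,3], whose mean is 3/2 = 1.5 and variance 3²/12 = 0.75. It never moves the dose by more than one step in these scenarios. The last row uses no alternative prior.

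If true rates are held at or above 5.5% (the placebo figure in Protocol 1.4), the exponential row becomes 60/59/51/50%, Unif[0,5] 6/30/53/63%, two or more steps 0.3/5/16/29%, and the ceiling row 3/25/51/65%.

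**Example with no TIE.** Under Unif[0,3] the path is 5, 8, 12, 19, 30, 30, 30 µg/kg. The posterior is proportional to prior × (1−0.08^β)³(1−0.135^β)³(1−0.22^β)³(1−0.325^β)³(1−0.43^β)⁹.

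| Prior | Mean beta | Fitted dose (µg/kg) | TIE rate at 30 µg/kg (95% interval) |
|---|---|---|---|
| Unif[0,3] | 2.53 | 30 | 11.8% (8.1–24.4%) |
| Gamma, matched | 3.00 | 37 | 8.0% (1.3–26%) |
| Exponential, mean 1 | 3.46 | 47 | 5.4% (0.4–24.9%) |
| Unif[0,5] | 3.85 | 47 | 3.9% (1.5–16.5%) |

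For Unif[0,3], 0.15^(1/2.53) = 0.47, and 0.43 at 30 µg/kg is the highest Table 3 rate below it. The lower limit of 8.1% is 0.43^2.98, against a floor of 0.43³ = 8.0%. This is an extreme outcome: no TIE in 21 subjects has probability of about 0/2/9/24% under the four curves.

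**The case against.** - **Little rests on this fit.** The sponsor ended the study and decided not to progress to a Phase 2 ICH study. In no enumerated scenario were 12 subjects on the estimated MTD by subject 21. This stands, and it keeps the point modest. A reader might infer that a declared MTD is unreliable, but SAP 5.2.4 provides for no declared MTD in that position.
- **The data are visible.** The SAP 6.1.1 figure overlays observed TIE proportions and numbers of subjects by dose, and the prior and Table 3 are printed. This also stands: a careful reader could refit the model. The curve and interval would still carry no sign of how much the prior supplies.
- **The size depends on the priors chosen.** The exponential and Unif[0,5] priors have means of 1 and 2.5, on either side of 1.5, so some change is nearly built in. For that reason the matched gamma is the fairest single comparison. On the SAP's own expected curve (beta = 1), Unif[0,5] changes only 6% of fits and the ceiling affects only 3%.
- **Refits can extrapolate.** The Unif[0,5] dose lies above the highest dose studied in 6/22/46/68% of trials, against 5/9/10/9% under Unif[0,3]. Any refit therefore needs a flag.
- **The SAP's sentence may be true at full size.** Over six assumed priors and six assumed curves, 47% of refits moved the dose at 21 subjects and 21% at 51. It is tempting to call the sentence false. Apart from the hard limit at 3, the supported statement is only that the trial stopped well short of that size.
- **Prior sensitivity may be in the simulation report.** That cannot be excluded, so the documents do not support saying that it was never examined.

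**Conclusion.** The point holds as a reporting gap that is cheap to close. At 21 subjects, a prior with the same mean and variance as the planned one but no ceiling moves the fitted dose by one grid step in about a quarter to a half of trials. More different priors move it in 6% to 86%, with shifts of two or more steps reaching 43% at beta = 2.5. The 8.0% and 16.6% floors follow from Table 3 and beta ≤ 3 alone and need no assumption about alternative priors.

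The ceiling affects the lower limit of the TIE-rate interval; on an MTD interval it would affect the upper limit. The percentages rest on the assumptions listed in the working, and the documents give no TIE counts.

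A reader might go further and conclude that Unif[0,3] is an error or that doses were wrongly assigned. The documents do not support that: the prior was tied to clinical input, and allocation also had escalation caps and eDMC oversight.

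**What to change.** Keep Unif[0,3] as the primary prior and change no allocation rule.

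- **SAP 6.1.1.1:** add a refit of the final TIE data under a prior matched in mean and variance but without the ceiling (for example gamma, mean 1.5, variance 0.75), and under at least one more dispersed or wider prior (for example exponential mean 1, or Unif[0,5]). Show the curves, intervals and estimated doses beside the SAP 6.1.1 figure.
- **Extrapolation:** flag any estimated dose above the highest dose studied as extrapolation, not a recommended dose.
- **Timing:** state that the alternative priors were chosen after the sponsor had seen open-label TIE data, since those data were reviewed after each cohort (SAP 2.2.2.2 and 7.2).
- **SAP 5.2.2:** state that 21 subjects may not overrule the prior, and disclose the floors of 8.0% at 30 µg/kg and 16.6% at 47 µg/kg.
- **Wording:** call any dose read from the fit an estimate, in line with SAP 5.2.4.

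The cost is two or three refits of existing data, one figure panel and a few sentences. The report may then show a range of doses instead of one, and the choice of priors remains a judgement.

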### 5.2.3. Allocation Rule

The allocation rule is designed to consistently pick the dose with TIE rate closest to but not exceeding the target 15%, therefore maximizing the number of subjects treated at or near that

dose. This is achieved by an adaptive allocation using the model-based estimate of TIE rate at each dose.

After the TIE data from the first cohort (5  $\mu\text{g/kg}$ ) becomes available, the prior distribution of  $\beta$  will be updated into a posterior distribution through Bayesian Markov Chain Monte Carlo (MCMC) simulations in Adaptive Design Explorer (ADE). The model-based MTD will be estimated as  $f^{-1}(0.15, \hat{\beta})$ , where 0.15 is the pre-specified target TIE rate at MTD and  $\hat{\beta}$  is the posterior mean of  $\beta$ . All subjects in the next cohort will be dosed at the dose level ( $d_j^*$ ) closest to this estimated MTD but not exceeding it, ie.

$$x_j^* = \max_j [x_j : x_j < f^{-1}(0.15; \hat{\beta})]$$
$$d_j^* \leftrightarrow x_j^*$$

If the current MTD estimate is above the highest dose so far tested, this allocation rule is subject to restriction of maximum 2 dose increments, as specified in Table 2. This restriction is built in the mCRM design module for dose recommendation.

As described in Section 2.2, extensive safeguards and monitoring for subject safety will be implemented. If treatment emergent modulation of one or more of the safety biomarkers fibrinogen, platelet count, and prothrombin time is observed that exceeds pre-specified thresholds during the interval from baseline to Day 4, dose increase will be limited to only one increment at a time. Other available safety data including clinically significant AEs or SAEs will also be assessed. *These events will not have any impact on mCRM-determined dose recommendations but may be used to inform dose assignments more conservative than those derived by the mCRM dose-toxicity model.*

#### 5.2.4. Stopping Rule

The dose-toxicity model is updated based on the frequency of TIEs in each completed cohort. This process is continued until at least one of the following stopping rules is met:

1. Maximum sample size of 51 subjects has been reached.
2. MTD has been identified with sufficient accuracy, ie, 12 subjects have been accumulated on a dose that is currently estimated to be the MTD by the fitted dose-toxicity curve.
3. All doses appear to be overly toxic and the MTD cannot be determined in the current trial setting (stop for futility).

If the stopping rule 1 is met but the stopping rule 2 is not met, not enough subjects have been studied to yield a model-based estimated MTD. If the stopping rule 2 is met, then the MTD will be identified as the current model-based estimated MTD. The earliest time point at which the trial could be stopped early and declare an MTD is after 20 subjects have been

treated and 12 at the MTD dose. For stopping rule 3, the futility stop can be made at any time.

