1.4. Study Rationale

This study will determine the maximum tolerated dose (MTD) of PF-05230907 and evaluate safety and tolerability of a single administration of PF-05230907 in subjects with spontaneous intracerebral hemorrhage (ICH). Given the severe morbidity and mortality associated with the condition and given the need to better define the maximum tolerated dose of PF-05230907 in order to plan future efficacy studies, a modified continual reassessment method (mCRM) will be implemented to determine the MTD (see [Section 9](#)) based on frequency of treatment emergent thromboembolic and/or ischemic events (to be referred to as TIEs throughout this document). A target TIE rate of 15% represents approximately a 5-10% increment above the background rate and is considered compatible with acceptable benefit risk in the high morbidity, high mortality indication of ICH. A background rate of approximately 5-10% in the ICH population is based upon published literature for spontaneous ICH from studies of activated coagulation factor VII in ICH and the placebo-treated subject-level datasets from 4 studies performed contemporaneously with the clinical studies of NovoSeven in ICH contained within the Virtual International Stroke Trial Archive (VISTA).^{7,8,9} The TIE rate in the internal analysis of the VISTA placebo datasets filtered to reflect the intended population for treatment with PF-05230907, was approximately 5.5% within the first 8 days from the baseline computed tomography (CT) scan.

Selection of the PD biomarkers included in the study (aPTT and PF1+2) is informed by the results from the study B2341001. The PD results will provide information on target engagement and coagulation pathway activation at the various dose levels studied.

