3.2. Progression to Subsequent Cohort

A target 15% TIE rate at the MTD will be employed for the MTD determination. The range of doses that may be explored will be from a grid of doses ranging from 1 $\mu\text{g}/\text{kg}$ to 47 $\mu\text{g}/\text{kg}$ ([Table 2](#)). Subjects will be enrolled in cohorts, starting with an initial dose of 5 $\mu\text{g}/\text{kg}$ for the first cohort (the highest dose safely administered in the first in human clinical study [B2341001]). If the modeled rate of TIEs at the 5 $\mu\text{g}/\text{kg}$ starting dose exceeds the pre-specified target toxicity rate of 15% for the MTD, lower doses may be explored. Starting with the second cohort, subjects will be assigned to a dose in the pre-defined dose grid that is closest to, but not exceeding, the currently predicted MTD based on a parametric dose-toxicity model that the mCRM utilizes to learn about the overall dose-TIE relationship subject to additional dose escalation constraints and clinical oversight. The dose-toxicity model is updated based on the frequency of TIEs in each completed cohort. Under the adopted mCRM design, the dose level for each subsequent cohort can be escalated, deescalated, or restudied but always aiming towards the MTD target based on the frequency of TIEs. However, dose level assignments may be modified to more conservative dose levels based upon sponsor medical judgment or eDMC recommendations. To prevent overly aggressive dose-escalation, the maximum allowed dose increase from the highest dose that has been previously studied is limited to 2 increments at a time (ie, not more than one dose level may be skipped-see ([Table 2](#)), which results in 50-67% increase in dose from the 5 $\mu\text{g}/\text{kg}$ dose and above. If treatment emergent modulation of one or more of the following laboratory safety biomarkers is observed during the interval from baseline to Day 4 (where available), as indicated below, dose increase will be limited to only 1 increment at a time (ie, no more dose skipping):

- Fibrinogen:
 - If baseline value is within normal reference range: a post-dose value $\leq 50\%$ of the lower limit of normal.
 - If baseline value $<$ lower limit of normal reference range: a post-dose value $\leq 50\%$ of the baseline value.
- Platelet Count:
 - If baseline value is within normal reference range: a post-dose value of $< 100,000$.

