## 5. GENERAL METHODOLOGY AND CONVENTIONS

### 5.1. Hypotheses and Decision Rules

This is a study to determine the MTD and assess the safety, tolerability, and PD of PF-05230907 administered once in subjects with ICH. No formal hypothesis testing will be performed. The decision rules for study stopping and MTD determination are described in Section 5.2.

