### 5.2. mCRM design

This study is designed to estimate the MTD, defined as the dose that yields approximately but no greater than the target 15% TIE rate. It employs a modified Continual Reassessment Method (mCRM) design, which utilizes Bayesian methodology to learn the dose-toxicity relationship continuously after each cohort's thromboembolic and/or ischemic event (TIE) data becomes available. Subjects will receive different doses using an adaptive allocation rule with the goal of estimating the MTD. Starting from the second cohort, subjects will be assigned to a dose, from a pre-defined dose grid, that is closest to but not exceeding, the current model-based estimate of MTD based on a one-parameter dose-TIE model, subject to additional dose escalation constraints described in Section 2.2.

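### Stopping rule 2 declares the MTD accurately identified on a headcount of 12, with no precision criterion and no TIE or higher dose required

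*SAP*

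**What the plan says.** SAP 5.2.4 lists three stopping rules. Rule 2 is: "MTD has been identified with sufficient accuracy, ie, 12 subjects have been accumulated on a dose that is currently estimated to be the MTD". The same section makes it binding: "If the stopping rule 2 is met, then the MTD will be identified as the current model-based estimated MTD". It also sets 20 treated subjects as the earliest point for such a declaration. SAP 2.2.4, Protocol 9.1 and the Protocol Summary repeat the accuracy claim. Protocol 3.4 gives the 12-subject condition without it.

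SAP 5.2 defines the MTD as "the dose that yields approximately but no greater than the target 15% TIE rate". Protocol 1.4 gives the background against which that target is set: "A background rate of approximately 5-10% in the ICH population is based upon published literature", and the sponsor's own placebo analysis "was approximately 5.5% within the first 8 days from the baseline computed tomography (CT) scan".

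Rule 1 is the maximum of 51 subjects. Rule 3 covers only the case where all doses look too toxic, and has no numeric threshold. No rule covers the case where no grid dose reaches 15%, although Protocol 1.5 foresees 47 µg/kg being tolerated with no MTD established.

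On uncertainty, SAP 6.1.1 plans a 95% band around the fitted dose-TIE curve. SAP 6.1.1.1 leaves an interval around the MTD optional.

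**The concern.** Rule 2 has two inputs: the number of subjects on a dose, and whether the current point estimate maps to that dose. Neither measures precision. The one-parameter curve always rises with dose, and each cohort goes to the current estimate, subject to the escalation cap. The headcount therefore tends to be reached whatever the true curve is. A trial can stop, and state that the MTD has been found accurately, with no TIE at the named dose and nothing tested above it.

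The declared MTD answers a primary objective, and Protocol 1.4 says it is needed to plan efficacy studies. A reader told that it is accurate would not know that the same declaration is likely when the drug adds no events, or how wide the plausible range of TIE rates at that dose is.

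**Working it through.** **Plan's own figures.** With Table 3 rates r, x = atanh(2r − 1) returns all 15 adjusted doses (largest difference 0.005), and 17 cohorts × 3 = 51. The documents state no probability of naming an MTD, so that has to be computed.

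**Inputs.** Table 3 rates and the Unif[0,3] prior (SAP 5.2.2); posterior-mean plug-in and cap of 2 levels above the highest dose tested (SAP 5.2.3); cohorts of 3 starting at 5 µg/kg; rule 2 at 12 subjects with at least 20 treated; maximum 51; target 15%; background 5.5%, range 5-10% (Protocol 1.4).

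**Model.** Setting x from Table 3 makes the TIE rate at dose i equal to r_i^β. The recommended dose is the highest with r_i^β̂ at or below 0.15, where β̂ is the posterior mean, subject to the cap.

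**Trial with no TIEs.** The path is fixed:

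| Cohort | Dose given (µg/kg) | Total N | β̂ | Next dose |
|---|---|---|---|---|
| 1 | 5 | 3 | 1.816 | 8 |
| 2 | 8 | 6 | 1.973 | 12 |
| 3 | 12 | 9 | 2.113 | 19 |
| 4 | 19 | 12 | 2.250 | 30 |
| 5 | 30 | 15 | 2.377 | 30 |
| 6 | 30 | 18 | 2.466 | 30 |
| 7 | 30 | 21 | 2.530 | 30 |
| 8 | 30 | 24 | 2.580 | stop, rule 2 |

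The model rate at 30 µg/kg is then 0.43^2.580 = 11.3%, and at 37 µg/kg 0.49^2.580 = 15.9%. So 30 µg/kg is declared the MTD on 0/24 TIEs, with 37 and 47 µg/kg untested.

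**Simulation.** Assumptions: no sponsor or eDMC override, no biomarker restriction, no replacements; rule 3 taken as no grid dose at or below 15%. The flat rates were run with 20,000 trials (standard error about 0.2 points), and all scenarios with 4,000.

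| True TIE rates | Rule 2 names an MTD |
|---|---|
| 5.5% at every dose | 94% |
| 10% at every dose | 91% |
| Table 3 (β = 1) | 94-95% |
| Table 3, β = 1.5 | 99% |
| Table 3, β = 2 | 99% |

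At a flat 5.5%, 39-40% of declarations have no TIE at the named dose and 85-86% have no higher dose tested.

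**Sensitivity of the flat 5.5% / 10% figures.** Single-level escalation throughout: 91% / 89%. No rule 3 stop: 95% / 97%. Headcount of 24: 46% / 45%, mainly because the 51-subject limit then ends most of the other trials. Posterior mean of the rate in place of the documented plug-in: 81% / 69%.

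**Role of the prior.** With β at most 3, the modelled rate at 47 µg/kg is never below 0.55³ = 16.6%, so the algorithm can never recommend that dose. About 70% of flat-5.5% declarations are at 30 µg/kg. With Unif[0,10], rule 2 still fires in about 90-91% at flat 5.5% and 89-91% at flat 10%. But about two thirds of the flat-5.5% declarations are then at 47 µg/kg.

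**Precision.** On the Table 3 curve, the median model 95% interval for the TIE rate at the declared dose is about 5-28%. Exact 95% intervals from 12 subjects alone are 0-26% for 0/12 (upper limit 1 − 0.025^(1/12)), 0.2-38% for 1/12 and 2-48% for 2/12.

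**The case against.** The best defence is that a stopping rule is meant to fire, so what matters is the dose it names. That dose does carry information: at flat 5.5%, 79% of declarations are at 24-30 µg/kg, against about 1% on the Table 3 curve. This stands, and it bars reading the firing rates as proof that the design cannot tell a harmless drug from a toxic one.

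A reader might also infer that the headcount gives a harmless drug a false ceiling at 30 µg/kg. The documents do not support that. The concentration there comes from the β ≤ 3 bound, a separate defect. With the wider prior, a dose below 47 µg/kg is named in about 30% of trials at flat 5.5% and about 60% at flat 10%.

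Other points stand in part:
- SAP 5.2.5 compared headcounts from 6 to 24 over six scenarios, so 12 was a considered choice. The documents claim only better average accuracy than 3+3, give no operating characteristics, and do not say whether any scenario kept every dose below 15%.
- A flat curve up to 47 µg/kg is a stress test. Protocol 1.3.1.2 reports thrombi in monkeys at higher doses. The Table 3 interval does not depend on the flat curve.
- SAP 6.1.1 already plans the 95% band, and Protocol 3.4 lets subjects be added to define the MTD further. Neither conditions the declaration or sets an accuracy criterion.
- "No formal hypothesis testing will be performed" (SAP 5.1). True, but the accuracy statement is still a claim about the primary result.

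**Conclusion.** The concern holds as a defect in what rule 2 concludes. It is not a case against stopping at 12. The rule declares accuracy without measuring it, and will usually do so when no dose reaches the target: about 94% of trials at flat 5.5% and 91% at flat 10%. Where the plan's own curve is true, the interval at the declared dose (about 5-28%) runs from the background range to nearly twice the target.

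These figures rest on the rules as written, an assumed rule 3 threshold and no overrides. The margin above 90% at flat 10% is thin. The zero-TIE path and the exact intervals need no simulation.

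A reader might infer that this trial's reported MTD is wrong. The documents do not show that. SAP Section 1 records termination after 21 subjects, SAP Table 1 records the decision not to progress to a Phase 2 efficacy study in ICH, and neither says whether rule 2 had been met. On the zero-TIE path it would not fire until 24. Practical effect is therefore limited, but the wording should still be corrected.

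**What to change.** Keep rule 2 unchanged as the enrolment stop. In SAP 5.2.4 and 2.2.4, Protocol 9.1 and the Protocol Summary:

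1. Delete the opening clause that asserts accuracy and keep the 12-subject condition, as Protocol 3.4 already words it. Call the result the model-based MTD estimate, and change the sentence in SAP 5.2.4 that identifies it as the MTD to match.
2. Replace the optional interval in SAP 6.1.1.1 with mandatory reporting, alongside the estimate, of: the 95% posterior interval for the TIE rate at that dose; the posterior probability that the rate exceeds 15%; the exact 95% interval from the observed TIEs at that dose; and whether any higher dose was tested.

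A reader might want the label of identified MTD to depend on the observed TIE proportion at and above the dose exceeding the 10% upper background. I do not recommend that cut-off. In simulation it keeps the label in about 64% of flat-10% declarations and withholds it in about a quarter when β = 2, where a grid dose (24 µg/kg, 0.38² = 14.4%) does meet the MTD definition.

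The cost is wording plus a few numbers from MCMC draws already produced and the observed counts. Dosing, enrolment and sample size do not change.
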